#### 11.1.3. Population of Interest

The primary pharmacodynamics analyses will be based on the Intent-To-Treat population, unless otherwise specified.

If there are protocol deviations that are thought to potentially impact the primary endpoints (defined as at least 10% of the ITT population being excluded from the PP population), an exploratory sensitivity analysis may be considered using the PP population.

Any such important protocol deviations will be identified before DBR and the subsequent sensitivity analysis on the PP population will be documented in the CSR.

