#### 11.1.4. Strategy for Intercurrent (Post-Randomization) Events

ABPM data is collected every 15 minutes for the first 6-hrs and then every 20 minutes thereafter until 24-hrs post dose. In order to reduce the extent of missing ABPM data due to device issues, the device is designed to retry measuring blood pressure if it fails to record a BP during the scheduled timepoint. In addition, after both Acute Challenge 1 and 2, the 24-hr ABPM results will be checked for data quality as defined in the Project Requirement Specification (PRS). If the ABPM fails the QC criteria following Acute Challenge 2, one additional Acute Challenge may be made in a subsequent, mid-week dialysis visit 1 week later if the participant agrees. This repeat Acute Challenge 2 would replace the failed QC Acute Challenge 2.

For these participants who have a failed QC of the ABPM for a given acute challenge day, the data that is available from the ABPM device will be used during a sensitivity analysis on the primary endpoint. For those participants that fail QC both Acute Challenge 2, and a repeat Acute Challenge 2, the repeat Acute Challenge 2 data will be utilized.

Since participants who discontinue randomized study medication are withdrawn from the study and would have already performed their Day 1 acute challenge, multiple imputation will be used to attempt to impute what the missing data would have been had the participant not stopped randomized study medication. These participants who are early withdrawn will have their missing Day 57 ABPM data imputed to be included in a sensitivity analysis on the primary endpoint. This sensitivity analysis will include those participants who both early withdrawal and have their ABPM data imputed as well as those participants whose ABPM data did not pass QC for a given day. Details of the multiple imputation can be found in Section 14.6.6.

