#### 11.1.5.2. Statistical Methodology Specification

Endpoint / Variables

 
Average of systolic blood pressure (SBP) as measured by ambulatory blood pressure monitoring (ABPM) over 6-hr post-dosing after 8 weeks (i.e. Day 57) of Hgb maintenance therapy
 

Model Specification

 
ANCOVA with terms for treatment, prior ESA dose (low/high), and post-HD/pre-Acute Challenge 1 SBP, difference between post-HD/pre-Acute Challenge 2 SBP and post-HD/pre-Acute Challenge 1 SBP, and treatment by (difference in post-HD SBP between Acute Challenge 1 and 2) interaction. Note that the pre-challenge SBP may change over time between Acute Challenge 1 and Acute Challenge 2 as a result of the maintenance therapy, and thus the pre-challenge SBP at Acute Challenge 2 is not a true pre-treatment covariate. As a result, the interpretation of the effect of the Acute Challenge 2 may be confounded by the impact of treatment phase on the covariate. Therefore, if the interaction term in this model is significant at the 0.10 level, then the primary model will be ANCOVA with terms for treatment, prior ESA dose (low/high), and post-HD/pre-Acute Challenge 1 SBP.
 

Model Checking & Diagnostics

 
Distributional assumptions underlying the statistical analyses will be assessed by visual inspection of residual plots. Normality will be examined by normal probability plots, while homogeneity of variance
 

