
 
A sensitivity analysis will be performed on the primary endpoint to include those subjects who stop randomized treatment and those participants who fail any QC for their acute challenge. 
 
The first group are those participants who stop randomized treatment. These participants will have their Day 57 6hr average SBP ABPM data imputed to assess what would have happened had the participant not stopped IP. Since these participants would have been randomized, there will be data for acute challenge 1, however acute challenge 2 data will need to be imputed. 
 
Post-HD/pre-Acute Challenge 2 SBP will also be imputed.
 
 
 
The second group are those participants who have QC failed either their Day 1 or Day 57 acute challenge, or QC failed both acute challenges. For this group no data imputation will be performed, instead the data that is available from the ABPM device will be used to calculate what the 6hr average is. 
 
Like for the primary endpoint, post-HD/pre-Acute Challenge SBP will be taken from the first measurement on the ABPM device. If missing, then the vital signs BP will be used instead.
 
 
 
 
 
Multiple imputation for the first group, those participants who stop randomized treatment, will be done under the assumption of a multivariate normal distribution using the Markov Chain Monte Carlo (MCMC) procedure assuming missing at random. 
 
Both the pre AC2 SBP and Day 57 6hr average SBP will be imputed
 
The first step will be to calculate the number of missing data points to see what the missing pattern is
 
Next the imputation phase will fill in values for the missing data points 
 
Seed code of 205665 will be used
 
Burn in iterations and maximum iterations are set to default, 200
 
This will result in 1,000 imputations being calculated
 
Trace plots and autocorrelation figures will be used to assess the imputations
 
Variables to be included for imputation: 
 
Day 1 6 hr average SBP from ABPM
 
Day 1 baseline SBP
 
Day 57 baseline SBP
 
Day 57 6 hr average SBP from ABPM
 
Add treatment and prior esa dose as by variables in proc mi 
 
If there are error and or warning messages related to the by statement, try by randomized treatment only until no error/warning messages.
 
 
 
Next the imputed dataset will be used to calculate the difference between the pre AC1 and pre AC2 SBP, now using the imputed pre AC2 SBP.
 
 
 
 
 
 
 
	

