## CONFIDENTIAL

205665

Pharmacodynamic and Biomarker: Tables					
No.	Population	IDSL / Example Shell	Title	Programming Notes	Deliverable
4.37.	ITT	PDT8	Summary of Analysis of Average 6hr ABPM SBP post-AC2, Imputed Data	Use imputed missing values for AC2 for early withdrawal subjects, calculate 6hr averages for those subjects who failed QC for any AC.  For subjects who AC2 failed QC, 6hr average SBP will be calculated without imputation	DR, SAC
4.38.	ITT	PDT3	Summary of Analysis of Average 8hr ABPM SBP post-AC2		DR, SAC
4.39.	ITT	PDT3	Summary of Analysis of Average 12hr ABPM SBP post-AC2		DR, SAC
4.40.	ITT	PDT3	Summary of Analysis of Average 24hr ABPM SBP post-AC2		DR, SAC
4.41.	ITT	PDT4	Summary of Analysis of AUEC SBP over 24hr post-AC2, Imputed Data	
 
If more than 25% of subjects are excluded from the ABPM AUEC analysis then this sensitivity analysis will be performed for the AC2 SBP AUEC model               
 
If during dry-run less than 25% of subjects are excluded, then table is not needed for dry-run
 
 
 
	SAC
Additional PD tables					
4.42.	ITT	PDT10	Summary of Subjects who QC Pass Acute Challenges	Column by treatment, row by Day 1 and Day 57, where Day 57 includes repeat AC2	SAC

CONFIDENTIAL

205665

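### The SAP should say that a failed Day 1 ABPM recording does not remove a subject with a valid Acute Challenge 2 recording from the primary analysis, and SAP 3.2 should not require a QC pass at both challenges

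*SAP*

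**What the plan says.** **Who enters the primary analysis.** SAP 11.1.3 states: "The primary pharmacodynamics analyses will be based on the Intent-To-Treat population, unless otherwise specified". The model in SAP 11.1.5.2 begins "ANCOVA with terms for treatment, prior ESA dose (low/high), and post-HD/pre-Acute Challenge 1 SBP", then adds the change in pre-challenge SBP and its interaction with treatment. It sets no QC condition. The QC condition is in SAP 14.6.6 (ABPM Data), which admits to the pharmacodynamic tables, figures and listings only subjects whose ABPM data pass QC. That sentence does not say which challenge is meant.

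**What the sensitivity analysis adds.** SAP 14.6.6 (Multiple Imputation) runs a sensitivity analysis on the primary endpoint to bring in subjects who stop treatment "and those participants who fail any QC for their acute challenge". Its second group is "those participants who have QC failed either their Day 1 or Day 57 acute challenge", or both. SAP 11.1.4 describes this group as "those participants whose ABPM data did not pass QC for a given day". The programming note to Table 4.37 says "calculate 6hr averages for those subjects who failed QC for any AC", and then "For subjects who AC2 failed QC, 6hr average SBP will be calculated without imputation".

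**How subjects are counted.** Protocol 9.2.1, SAP 2.3 and SAP 14.7.1 count or replace on an AC2 QC pass, with a target of 25 per arm. Protocol 9.2.3 replaces on completing AC2. SAP 3.2 instead lists, as a step before the final analysis, that all participants (N=50) have completed the study and passed QC at both challenges. Protocol 4.1 and 7.5.1 and SAP 11.1.4 allow one repeat after a failed AC2 recording. Nothing allows a repeat of AC1.

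**The concern.** A subject can have an unusable Day 1 recording and a good Day 57 recording. If a sensitivity analysis is needed to bring that subject in, the subject was outside the primary analysis. A programmer who applies the subject-level sentence in SAP 14.6.6 would then leave out a valid value of the primary endpoint because of a recording the endpoint does not use. Another programmer, working from the ITT population and the AC2-only counts, would keep the subject. The trial is open-label, so membership of the primary set should be fixed in writing before the data are analysed.

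Separately, recruitment can stop correctly at 25 AC2 passes per arm while the SAP 3.2 condition is unmet. A failed AC1 recording cannot be redone, and the SAP does not say what happens then.

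**Working it through.** **1. What the primary model needs from Day 1.** It needs one reading, the post-dialysis, pre-AC1 SBP. SAP 14.6.6 takes this from the first ABPM measurement if that is usable and close enough to the device start time. Otherwise it uses the post-dialysis vital sign. A valid AC2 record can therefore be analysed without a QC-passed Day 1 recording.

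**2. The passages side by side.**
- Towards exclusion: the subject-level display rule in SAP 14.6.6; the sensitivity group in SAP 14.6.6 and 11.1.4; the first sentence of the Table 4.37 note.
- Towards QC by challenge: the ITT population (SAP 11.1.3); no QC condition in SAP 11.1.5.2; the day-specific wording in SAP 11.1.4; the repeat rule, under which a failed original Day 57 recording is dropped but the subject stays in; Table 4.42, which tabulates QC passes in separate Day 1 and Day 57 rows, with the repeat counted under Day 57; the second sentence of the Table 4.37 note; the AC2-only counts in Protocol 9.2.1 and SAP 2.3 and 14.7.1.

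**3. The plan's own power figure.** Inputs from Protocol 9.2.1: difference 15 mmHg, SD 16 mmHg, 25 per arm, 5% significance level; two-sided, from the two-sided 95% CI in Protocol 9.4.1. Power comes from the noncentral t with 2n − 2 degrees of freedom and noncentrality 15 / (16 × √(2/n)). The half-width is t(0.975, 2n − 2) × 16 × √(2/n). At n = 25 power is 90.1% and the half-width 9.10 mmHg, matching the stated 90% and 9.1 mmHg.

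**4. Effect of the exclusion reading.** The Day 1 failure rate q is an assumption. The mean number left per arm is 25 × (1 − q): 23.75 at 5%, 22.5 at 10% and 21.25 at 15%.

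| n per arm | Power, unadjusted | 95% CI half-width (mmHg) |
|---|---|---|
| 25 | 90.1% | 9.10 |
| 24 | 88.9% | 9.30 |
| 23 | 87.5% | 9.51 |
| 22 | 85.9% | 9.74 |
| 21 | 84.2% | 9.98 |

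**5. Covariate adjustment.** Take SD 16 as the unadjusted SD, use a residual SD of 16 × √(1 − R²), and give up 4 degrees of freedom for covariates. A multiple correlation R of 0.21, 0.30, 0.36 or 0.41 then restores 90.1% at 24, 23, 22 or 21 per arm. This is an approximation.

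**6. The SAP 3.2 condition.** If exactly 50 subjects pass AC2 and failures are independent, the chance that all 50 also passed AC1 is (1 − q)^50: 60% at q = 1%, 36% at 2%, 7.7% at 5%. If recruitment overshoots and the condition is read as at least 50 passing both, the chance is much higher. With 52 AC2 passers and q = 2% (at most 2 failures) it is 91%; with 54 and q = 5% (at most 4 failures) it is 87%.

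**The case against.** The best defence is that the SAP already treats QC by challenge day. Table 4.42 holds it that way, SAP 11.1.4 speaks of a given day, and the repeat rule attaches QC to the recording. Day 1 failures also have a good reason to be named in the sensitivity analysis whatever the primary rule. The imputation model uses "Day 1 6 hr average SBP from ABPM", so those subjects need a rule for that variable, and SAP 11.2.4 may extend the approach to secondary endpoints, which include Day 1 averages. The QC criteria are in the Project Requirement Specification, which is not part of these documents. SAP 3.2 is a timing step that changes no population or model.

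Much of this stands. A reader might infer that the SAP plainly excludes Day 1 failures from the primary analysis; the documents do not support that, and the per-challenge evidence is substantial. The defence is still an inference. The one sentence that sets the QC condition for displays names no challenge, and the sensitivity text, read as written, presupposes exclusion. That SAP 3.2 is only about timing limits the consequence but does not remove its conflict with the counting rules.

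**Conclusion.** The texts conflict and should be corrected before database freeze. The primary set after a Day 1 QC failure rests on inference, and the literal reading of the sensitivity text would leave out valid Day 57 records. SAP 3.2 contradicts Protocol 9.2.1 and SAP 2.3 and 14.7.1, and its condition cannot be repaired for AC1.

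The size is modest and uncertain. A reader might infer that the trial is underpowered; it is not shown to be. The stated 90% holds at 25 per arm, and inclusion on AC2 QC leaves that number unchanged. Under exclusion, the loss is about 1 percentage point at 24 per arm and between 2 and 3 at 23, before any gain from covariates. All of it rests on a Day 1 failure rate that the documents do not give. A reader might also take the (1 − q)^50 figures as the chance of meeting SAP 3.2; they apply only if exactly 50 subjects pass AC2, and a small overshoot changes them greatly.

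**What to change.** - In SAP 11.1.4 and 14.6.6, including the sentence that limits the pharmacodynamic displays, state that the primary analysis includes every ITT subject with a QC-passed AC2 or repeat AC2, whatever the AC1 QC result.
- Take pre-AC1 SBP from a usable Day 1 ABPM zero reading, or otherwise from the post-dialysis vital sign that SAP 14.6.6 already allows.
- Change the SAP 3.2 condition to an AC2 QC pass.
- Keep the available-data rule for Day 1 failures, which the imputation model and any AC1 sensitivity analyses need.

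The cost is SAP wording and one inclusion flag, with no new data or visits. The downside is that a few baselines would be cuff readings or would come from a QC-failed Day 1 recording. If the sponsor prefers to require both passes, recruitment and replacement must count both. At an assumed 5% or 10% Day 1 failure rate that means 27 (25/0.95, rounded up) or 28 (25/0.90, rounded up) AC2 passers per arm.

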9.2. Sample Size Considerations

9.2.1. Sample Size Assumptions

It is expected that 31 subjects will be randomized into each treatment arm. Assuming a 20% withdrawal rate during the Hgb Maintenance Period, there will be 25 subjects per treatment arm that will undertake Acute Challenge 2. The study will continue to recruit subjects until it is projected that 25 subjects per treatment arm complete and pass QC for Acute Challenge 2.

Assuming a 5% significance level and a true standard deviation (SD) of 16 mmHg for average SBP over 6 hours, a sample size of 25 subjects per treatment group will provide greater than 90% power to detect a -15 mmHg difference between treatment groups. Under these assumptions, statistical significance will be obtained if there is more than a 9.1 mmHg mean difference observed in favor of daprodustat.

Table 6 Power and Half-width of 95% CI for pair-wise comparisons, assuming a 16 mmHg SD for average SBP over 6 hours

Challenge	Expected Number of Subjects per Treatment Group	Power to detect 15 mm Hg difference	Half-Width of 95% CI ²
Acute Challenge 1	31	95%	8.1 mmHg
Acute Challenge 2 ¹	25	90%	9.1 mmHg

¹ Primary Comparison² Minimal detectable effect

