9.4. Key Elements of Analysis Plan

9.4.1. Primary Analyses

The primary analysis of average SBP over 6 hr post-dose during Acute Challenge 2 will be an analysis of covariance (ANCOVA) with terms for treatment, prior ESA dose (low/high), and post-HD/pre-Acute Challenge 1 SBP, difference between post-HD/pre-Acute Challenge 2 SBP and post-HD/pre-Acute Challenge 1 SBP, and treatment by (difference in post-HD SBP between Acute Challenge 1 and 2) interaction. Note that the pre-challenge SBP may change over time between Acute Challenge 1 and Acute Challenge 2 as a result of the maintenance therapy, and thus the pre-challenge SBP at Acute Challenge 2 is not a true pre-treatment covariate. As a result, the interpretation of the effect of the Acute Challenge 2 may be confounded by the impact of treatment phase on the covariate. Therefore, if the interaction term in this model is significant at the 0.10 level, then the primary model will be ANCOVA with terms for treatment, prior ESA dose (low/high), and post-HD/pre-Acute Challenge 1 SBP. The primary model will provide a point estimate and two-sided 95% CI for the treatment effect and a p-value for the superiority assessment. Superiority will be established if the p-value is <0.05.

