**CONFIDENTIAL**

205665

will be assessed by plotting the residuals against the predicted values for the model. If assumptions are grossly violated, alternative analyses will be considered.
Model Results Presentation

 
The point estimate, two-sided 95% CI and p-value for the difference between treatment groups will be presented from the selected final model for the superiority assessment. Superiority will be established if the p-value is <0.05.
 

Sensitivity and Supportive Analyses

 
If there are protocol deviations that are thought to potentially impact the primary endpoints (defined as at least 10% of the ITT population being excluded from the PP population), an exploratory sensitivity analysis will be completed. The analysis used for the primary endpoint will be repeated and similar results will be presented.
 
Participants who discontinue randomized study medication early will have their missing Day 57 AC2 ABPM data imputed; a sensitivity analysis will be run on the primary endpoint including these participants.
 
The primary endpoint will analyse using a 6-hour average of BP from ABPM device, sensitivity analyses using 8, 12, and 24-hour averages will be analysed using the primary model explained above in the model specification section.
 

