**CONFIDENTIAL**

205665

Challenge 1 and 2) interaction. Note that the pre-challenge ABPM (DBP/MAP/HR) may change over time between Acute Challenge 1 and Acute Challenge 2 as a result of the maintenance therapy, and thus the pre-challenge ABPM (DBP/MAP/HR) at Acute Challenge 2 is not a true pre-treatment covariate. As a result, the interpretation of the effect of the Acute Challenge 2 may be confounded by the impact of treatment phase on the covariate. Therefore, if the interaction term in this model is significant at the 0.10 level, then the primary model will be ANCOVA with terms for treatment, prior ESA dose (low/high), and post-HD/pre-Acute Challenge 1 ABPM (DBP/MAP/HR).
 
 
For the second secondary endpoint, AUEC of SBP, DBP, HR, and MAP post-acute challenge 1 and 2 will be analyzed using an ANCOVA model with terms for treatment and prior ESA dose (low/high).
 
The AUEC for ABPM will only be analysed if a subject has ABPM data up to hour 24. 
 
For example if the subject has ABPM data up to hour 23, the subject will be excluded from the ABPM AUEC analysis.
 
If more than 25% of subjects are excluded from the ABPM AUEC analysis because the subject is missing any of the 3 possible hour 24 ABPM measurements, then an extrapolation technique of average hour 23 measurement carried forward to hour 24 may be utilized as a sensitivity analysis for AUEC ABPM.
 
 
 

Model Checking & Diagnostics
 
 
Distributional assumptions underlying the statistical analyses will be assessed by visual inspection of residual plots. Normality will be examined by normal probability plots, while homogeneity of variance will be assessed by plotting the residuals against the predicted values for the model. If assumptions are grossly violated, alternative analyses will be considered.
 
Section 14.6.6 outlines any transformation of data as needed.
 

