
CONFIDENTIAL

205665

Pharmacodynamic and Biomarker	

 
○ The analysis phase will then calculate what the parameter estimates are using the same model as the primary endpoint, ANCOVA model with terms for treatment, prior ESA dose (low/high), pre AC1 SBP, difference between pre AC1 and pre AC2 SBP, and interaction of treatment and difference between pre AC1 and pre AC2 SBP. 
 
▪ if the interaction term in this model is significant at the 0.10 level, then the model will be an ANCOVA with terms for treatment, prior ESA dose (low/high), and pre AC1 SBP, just like the primary endpoint
 
 
 
○ The pooling phase will then pool all 1,000 model's parameter estimates.
 
● After the sensitivity analysis pooled parameter estimates are calculated, output will be compared with original non-imputed model (primary endpoint). 
 
○ Day 57 6hr average SBP values will be computed and compared across treatment groups using the primary ANCOVA model described above. Rubin's rules [Rubin, 1987] will be used to combine results of the imputed datasets using SAS PROC MIANALYZE procedure. As a result, a single estimated treatment difference and its standard error will be produced, with which a 95% CI will be calculated.
 
○ For each parameter, the estimate, 95% CI, and p-value will be compared
 
○ If the results of the primary endpoint differs when compared with this sensitivity analysis, then further secondary endpoint sensitivity analyses will be analysed in a similar fashion.
 
 
 
	
Biomarker Derivations	

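### The imputation sensitivity analysis applies the 0.10 interaction rule before pooling, so 1,000 fits of two different models may be combined; the other sensitivity analyses of the primary endpoint do not say whether the rule is re-tested

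*SAP*

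**What the plan says.** SAP 11.1.5.2 defines two models for 6-hour average SBP at Acute Challenge 2 (AC2). The full model has treatment, prior ESA dose, pre-Acute Challenge 1 (AC1) SBP, the AC2-minus-AC1 difference in pre-challenge SBP, and treatment by that difference. The reduced model keeps only the first three terms. The switch is: "if the interaction term in this model is significant at the 0.10 level, then the primary model will be ANCOVA".

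The same section lists the sensitivity analyses. For other time windows, "sensitivity analyses using 8, 12, and 24-hour averages will be analysed using the primary model explained above in the model specification section". The per-protocol analysis repeats the primary analysis.

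SAP 14.6.6 (Multiple Imputation) describes an imputation phase giving 1,000 completed data sets, an analysis phase and a pooling phase. The analysis phase fits the full model and adds, as a sub-item, "if the interaction term in this model is significant at the 0.10 level, then the model will be an ANCOVA with terms for treatment". The next step is: "The pooling phase will then pool all 1,000 model's parameter estimates". The text then promises one estimated treatment difference by Rubin's rules and a parameter-by-parameter comparison with the primary output. If the two results differ, sensitivity analyses of the secondary endpoints follow (also SAP 11.2.4). No threshold for differing is given.

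No section says that the model form chosen for the primary result is carried forward.

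**The concern.** The two models do not estimate the same effect. The full model conditions on the change in pre-challenge SBP, which the SAP itself says is not a true pre-treatment covariate. The reduced model conditions only on the AC1 value. If maintenance therapy moves pre-challenge SBP differently in the two arms, the full model removes that part of the effect and the reduced model keeps it.

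Rubin's rules combine repeated estimates of one quantity. If the 0.10 test is made within each completed data set, the pooled figure is a weighted mixture with no single estimand, and the between-imputation variance includes the jump between models as well as the uncertainty from missing data. In sets that switch, the difference and interaction terms do not exist, so those parameters lack the 1,000 estimates that the comparison presupposes.

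The purpose of the analysis is to show whether missing data matter. A gap from the primary could instead come from a change of model, and it would trigger further analyses. The same holds for the 8, 12 and 24-hour and per-protocol analyses if the rule is re-tested there: a gap might reflect the model and not the window or the population.

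**Working it through.** **1. Design figures (Protocol 9.2.1).** Inputs: two-sided 5% level, SD 16 mmHg, 25 per arm, difference 15 mmHg.
- Standard error = 16 × √(2/25) = 4.525.
- Half-width = t(0.975, 48 df) × SE = 2.011 × 4.525 = 9.10 mmHg (plan: 9.1).
- Power from the noncentral t with noncentrality 15/4.525 = 3.31 is 0.901 (plan: above 90%).

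**2. How many cases are imputed.** Protocol 9.2.1 assumes 31 randomized per arm and 20% withdrawal: 0.20 × 31 ≈ 6 per arm. Three per arm was also run.

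**3. How far apart the two models are.** Let δ be the treatment effect on pre-AC2 SBP and b the slope of the 6-hour average on the difference. With no interaction, full minus reduced effect = −b × δ. If the four SBP variables (both pre-challenge values and both averages) have equal SD and common correlation r, then b = r/(1+r). Neither r nor δ is in the documents. Values of 5 and 8 mmHg for δ are borrowed from the range Protocol 2.1 gives for SBP rises on ESAs.

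| r | b | δ = −5 | δ = −8 |
|---|---|---|---|
| 0.3 | 0.231 | 1.2 | 1.8 |
| 0.6 | 0.375 | 1.9 | 3.0 |
| 0.8 | 0.444 | 2.2 | 3.6 |

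The simulation below gave 1.2–2.4 and 1.7–3.7 mmHg, in agreement. With δ = 0 the average gap is about 0. With δ = −8 and an interaction slope of 0.3 it is 2.9–4.8.

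**4. Frequency and size of mixing if the test is made per imputation.** Assumed: 31 per arm; 3 or 6 missing per arm completely at random; multivariate-normal imputation by treatment; 1,000 imputations; 120 trials per scenario; r = 0.3, 0.6, 0.8; δ = 0, −5, −8; interaction slope 0, or 0.3 with δ = −8; treatment effect read at the mean difference.

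| Result over scenarios | 3 missing/arm | 6 missing/arm |
|---|---|---|
| Both models pooled | 77–92% | 98–100% |
| Minority model ≥1% of fits | 35–65% | 77–87% |
| Minority model ≥10% of fits | 16–37% | 27–57% |
| Mean absolute shift, mixed vs one model | 0.06–0.50 mmHg | 0.08–1.05 mmHg |

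The largest shift in a single trial was 5.4 mmHg.

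**5. Effect on conclusions.** A second simulation used variance components instead: SDs of 12 between subjects, 8 day to day, 10 for a single reading and 7 residual. The total for the average is √(144+64+49) = 16.0. It had 6 missing per arm, 1,000 trials and 100 imputations. In 46% of trials between 5% and 95% of imputed sets chose the reduced model.

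| True effect | Rejection rate, mixed vs one model | Significance verdict changed |
|---|---|---|
| 0 | 2.7% vs 4.0% | 1.3% |
| −8 mmHg | 65% vs 70% | 5.5% |
| −15 mmHg | 98.6% vs 98.8% | 0.4% |

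**6. Other windows.** With 25 per arm, no true interaction and a re-test, the 6-hour analysis and a longer-window analysis choose different models in about 5–10% of trials (assumed residual correlation 0.95–0.80).

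**The case against.** The best defence is that SAP 14.6.6 never says that the test is made in each imputed data set. It speaks of the same model as the primary endpoint, and a parameter-by-parameter comparison presupposes the same parameters in both outputs. SAP 11.1.5.2 likewise refers to a selected final model, so the 8, 12 and 24-hour analyses may inherit it. This stands as an ambiguity, but it does not remove the point. If the form were already fixed, the imputation text would need no condition, and the condition sits before the pooling step. A programmer could follow either reading.

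The second defence is that the consequence is small. Average shifts are about 1 mmHg or less, and in the run with variance components mixing was conservative under no effect. This stands, and it lowers the grade.

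A reader might infer that the rule is re-run in every AC2 analysis. It is not: the AUEC models (SAP 11.2.5.1) and the exploratory Cmax models (SAP 11.3.1.1) have fixed terms.

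A reader might also count the separate rule for DBP, MAP and HR in SAP 11.2.5.1 as the same fault. That text deliberately gives each parameter its own pre-challenge terms and its own test. SAP 5.5 treats secondary tests as exploratory. Whether linked parameters should share a form is a matter of judgement and not an error in the plan.

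**Conclusion.** The point holds for the imputation analysis: as naturally read, SAP 14.6.6 lets Rubin's rules pool full and reduced models, and with about 6 missing per arm that is very likely. The plan does not state that it will pool two models, so the exact charge is that its text permits this and suggests it. For the 8, 12 and 24-hour and per-protocol analyses the charge is only that re-testing is left unstated.

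The main harm is to interpretation: a sensitivity result without one estimand, compared with a primary result that has one. The average numerical shift was 0.06–1.05 mmHg against a half-width of 9.1 mmHg. The simulation figures rest on correlations, shifts and a missingness mechanism that the documents do not give, and are illustrative ranges. The primary estimate, interval and superiority test do not pass through this step, so a claim that the primary result is compromised is not supported. Grade: SHOULD-FIX.

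**What to change.** In SAP 14.6.6, delete the repeated 0.10 test and state that the model form selected in the observed-data primary analysis of 6-hour SBP is fitted to all 1,000 imputed data sets. In SAP 11.1.5.2, add that the same form is used for the per-protocol and the 8, 12 and 24-hour analyses, without re-testing the interaction. Leave the rule for DBP, MAP and HR in SAP 11.2.5.1 as it is.

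Mixing is then zero by construction, and differences from the primary can no longer come from a switch of model form. The cost is about two sentences, with no new data or tables and no change to the primary power statement.
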